4. PARTICIPANT ENTRY

After the fully informed consent has been obtained in writing with the opportunity to ask questions, patients' participation will begin with the visit to the hospital where they will attend their phasing test, as part of their standard care. Following completion of the phasing they will proceed to do their water drinking test which will be followed by several measurements of their IOP and other relevant outcomes. Once they have completed the water drinking test and all necessary measurements their participation in the study will end and their care will continue as normal. Participation in this (active) part of the study will only last 1 day (single visit to the hospital).

4.1 INCLUSION CRITERIA

- Able to give informed consent to participate in the study
- Aged between 18 and 80 years of age
- Clear optical media
- Spherical equivalent +10D
- Primary open-angle glaucoma or normal tension glaucoma proven by visual field testing or OCT imaging combined with clinical assessment.

4.2 EXCLUSION CRITERIA

- Have any other known ocular disease (except glaucoma)
- Have serious cardiac or kidney disease (WDT contra-indication)
- Have swallowing difficulties associated with either a neurological or gastrointestinal condition.

- Patients with any contra-indication of drinking large amounts of water in a small period of time e.g. swallowing impairment, oesophageal stricture, gastric banding.
- Have secondary or narrow/closed angle glaucoma
- Patients submitted to any surgical procedure or laser intervention during the evaluation period
- Participants who are involved in other current research

4.3 WITHDRAWAL CRITERIA

Participants who lose mental capacity and those who may find it difficult to adhere to the study protocol will be withdrawn. Due to the short duration and low risk-profile of the study there are no stopping criteria.

If a participant loses capacity to consent during the course of the study, they would be withdrawn from the study, while the identifiable data already collected with consent would be retained and used in the study. No further data would be collected or any other research procedures carried out on or in relation to the participant.

5. ADVERSE EVENTS

5.1 DEFINITIONS

Adverse Event (AE): any untoward medical occurrence in a patient or clinical study subject.

Serious Adverse Event (SAE): any untoward and unexpected medical occurrence or effect that:

- **Results in death**
- **Is life-threatening** – refers to an event in which the subject was at risk of death at the time of the event; it does not refer to an event which hypothetically might have caused death if it were more severe
- **Requires hospitalisation, or prolongation of existing inpatients' hospitalisation**
- **Results in persistent or significant disability or incapacity**
- **Is a congenital anomaly or birth defect**

Medical judgement should be exercised in deciding whether an AE is serious in other situations. Important AEs that are not immediately life-threatening or do not result in death or hospitalisation but may jeopardise the subject or may require intervention to prevent one of the other outcomes listed in the definition above, should also be considered serious.

5.3 REPORTING PROCEDURES

All adverse events should be reported. Depending on the nature of the event the reporting procedures below should be followed. Any questions concerning adverse event reporting should be directed to the Chief Investigator in the first instance.

5.3.1 Non serious AEs

All such events, whether expected or not, should be recorded.

5.3.2 Serious AEs

All SAEs should be reported to the <name of REC> where in the opinion of the Chief Investigator, the event was:

- 'related', ie resulted from the administration of any of the research procedures; and

- 'unexpected', ie an event that is not listed in the protocol as an expected occurrence

Reports of related and unexpected SAEs should be submitted within 15 days of the Chief Investigator becoming aware of the event, using the NRES SAE form for non-IMP studies. The Chief Investigator must also notify the Sponsor of all SAEs.

Local investigators should report any SAEs as required by their Local Research Ethics Committee, Sponsor and/or Research & Development Office.

Contact details for reporting SAEs

[contact]

CI email ([contact])

[contact], attention [name]

Please send SAE forms to: ICORG CTU Western Eye Hospital, [name]
[name]

[contact] (Mon to Fri 09.00 – 17.00)

6. ASSESSMENT AND FOLLOW-UP

Following completion of the study, participants will be followed up in their usual clinic as part of their regular care. The participants' follow-up data such as OCT scans, Visual Field tests, mDTCs and WDTs, which is routinely generated as part of the glaucoma care pathway will be accessed for 18 months following completion of participation with a view of correlating initial results with possible disease progression and other related outcomes. This segment of the study is purely data-based and does not require any active involvement from patients. Participation is optional, and patient's decision (whether or not to grant access to the data) will be documented in the informed consent form.

End of study is defined as last patient last visit (LPLV)

7. STATISTICS AND DATA ANALYSIS

7.1 Sample size

In this pilot study we aim to recruit a total of 40 glaucoma patients.

This is based on a power calculation of giving 80% power to detect a 2 mmHg difference in IOP peak (sd 2 mmHg) with $\alpha = 5\%$.

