1.1.6. Previous studies

Previous studies have shown correlation between the water drinking test and the modified diurnal tension curve^[24]. Vasconcelos-Moraes CG et al.^[24] showed that the WDT peak was significantly correlated with the mDTC peak (Person's Correlation Coefficient $r=0.780$ for a 95% confidence interval between 0.716 to 0.831, $p<0.0001$), however this has not yet been widely reproduced. However, this study was conducted on POAG patients who were on topical therapy for raised intraocular pressure, and therefore were required to undergo a washout period of no medication.

Figure 2

Correlation between IOP peaks during the WDT and mDTC

This study showed 95% limits of agreement between the WDT and mDTC IOP peaks ranging from -3.9 mmHg to 8.2 mmHg. In 52.5% of the tests, the agreement was within ± 2 mmHg.

[figure not shown]

Figure 3

Agreement between the WDT and mDTC peaks

Eighty-two percent of eyes showed higher IOP peaks during the WDT than the mDTC (95% confidence interval between 0.0 and 6.99 mmHg).

When analysing glaucomatous progression De Moraes *et al.*^[9] showed that higher IOP peaks during the WDT were predictive of future visual field progression (hazard ratio=1.11; 95% confidence interval, 1.02 to 1.21; P=0.013), but also that the average and peak IOP during office hours over the same follow-up period were not significantly associated with progression (P=0.651 and 0.569, respectively). This study showed that IOP peaks detected with the WDT were predictive of future visual field progression in a treated POAG population, while office hours measures were not.

Another study performed by Yoshikawa *et al.*^[16] in normal tension glaucoma patients showed that the maximum IOP levels after the water drinking test in patients with progressive visual field loss was significantly greater than the levels observed for the non-progressive group. Given that a common indication for referring patients for the mDTC is disease progression despite normal pressures off-treatment ('normal-tension glaucoma'), the agreement of the two tests in this specific cohort is currently under-documented.

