2. STUDY OBJECTIVES

- **Primary research objective** is to investigate the correlation and agreement between the intraocular pressure peaks detected during the water drinking test and the standard phasing test.

Secondary research objective is to correlate the IOPs obtained with both tests and prognostic outcome of the patients enrolled in the study to see whether these methods have predictive value for glaucoma progression. We will also measure autonomic nervous system activation (pupil size, heart rate and postural BP) during the test to investigate one possible mechanism behind it.

Lay summary

Raised intraocular pressure (IOP) is the main risk factor for the development and progression of glaucoma. The mDTC is a test that consists of four to five eye pressure measurements taken throughout office hours to check for rises in pressure that may be missed during their clinic appointment. To better try to assess the IOP peaks in a more time-efficient way, the water-drinking test has been developed. This involves the patient drinking a weight-adjusted volume of water within 5 minutes which has the effect of testing the ability to cope with increased demand for fluid to leave the eye. It is unclear as to the physiological mechanism by which this occurs. In this study we aim to compare the eye pressure measurements with both tests, and to see if either have any bearing on whether the patient's disease is getting worse. We also aim to show the changes in blood pressure and heart rate throughout the test.

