3. STUDY DESIGN

As described below active participation in the study (involving a single visit to the hospital) will last a total of 1 day, while the access (and analysis) of follow-up data generated as part of routine care pathway will go on for a period of 18 months in total. Participants are not required to do anything during this segment of the study.

- Observational cohort study
- 40 Primary open-angle and normal tension glaucoma patients will be attending a single visit lasting 9 hours.
- Their usual follow-up data will be tracked for 18 months

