3.1.2. Interventions

Baseline and qualification assessments will take place on the day of the study. These include a medical, ophthalmic and drug history, ophthalmic examination, postural blood pressure measurement, testing of visual acuity, OCT/OCTA of the optic disc and macula and then IOP assessment. All ophthalmic assessments will be done on both eyes using the Heidelberg Spectralis® imaging system. The mDTC will be conducted as part of patient's regular visit and is standard of care which consists of 5 IOP measurements beginning at 8am and 2 hourly afterwards (+/- 15min). Following completion of mDTC patients will have their WDT as detailed below.

The water drinking test will occur following the mDTC and will involve the patient drinking 800mL of water at room temperature, within a maximum of five minutes, after a period of no fluid intake of at least 2 hours. This will come after a period of no fluid intake of at least 2 hours (2pm onwards). For the WDT, the first IOP measure will correspond to the last mDTC measure, and three IOP measurements will be made after water intake with a 15-minute interval between each. IOP measurements will be recorded using Goldmann Applanation Tonometry (GAT). At each 15 minute interval, postural blood pressure, heart rate, oxygen saturations and pupil diameter will be measured. The ambient light conditions will be monitored with a light meter. Imaging will then be repeated after one hour of the test.

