7.4.3 Statistical analysis

No interim analyses will take place as part of this pilot study. Data will be acquired using integrated Heidelberg® software packaged with the Heidelberg® Spectralis OCT system. Data for this initial pilot study will be collected using Microsoft® Excel, and analysed using R and GraphPad prism to compare IOPs between the mDCT and WDT.

Specific analyses will include:

- Generation of baseline data including mean and standard deviation of baseline characteristics
- Bland-Altman agreement analysis of the primary outcome
- Correlation analysis between WDT and rate of progression.
- Analysis of change in OCT measurements
- Change over time analysis for secondary outcomes compared to baseline

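### The power calculation in section 7.1 does not produce 40 patients: in this paired design its inputs need 10 to 18 and give over 99% power at 40

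*Combined protocol and SAP*

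**What the plan says.** Section 7.1 states: "In this pilot study we aim to recruit a total of 40 glaucoma patients". It then gives the basis: "This is based on a power calculation of giving 80% power to detect a 2 mmHg difference in IOP peak (sd 2 mmHg"). The significance level is 5%. It names no test, sidedness, correlation or dropout allowance. It does not say whether the SD belongs to the within-patient difference or to a single test's peak, and it cites no source for it.

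The design is one cohort. Section 3: "40 Primary open-angle and normal tension glaucoma patients will be attending a single visit lasting 9 hours". Section 3.1.2: "Following completion of mDTC patients will have their WDT as detailed below". There is no second group.

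The primary objective in section 2 "is to investigate the correlation and agreement between the intraocular pressure peaks detected during the water drinking test and the standard phasing test". Section 7.4.3 lists "Bland-Altman agreement analysis of the primary outcome".

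Section 1.1.6 gives the only figures in the document on how the two peaks differ: "This study showed 95% limits of agreement between the WDT and mDTC IOP peaks ranging from -3.9 mmHg to 8.2 mmHg", and "Eighty-two percent of eyes showed higher IOP peaks during the WDT than the mDTC". It also reports a correlation of 0.780 between the two peaks.

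**The concern.** A difference equal to one SD is a large effect for a paired comparison, and 40 pairs is far more than 80% power would normally require. If the inputs do not lead to 40, a reader cannot tell which of the SD, the design or the power is not what the authors used.

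The calculation also concerns only a mean difference, which in a Bland-Altman analysis is the bias. The objective is agreement and correlation. Whether one test can stand in for the other depends mainly on the width of the limits of agreement, and section 7.1 does not say how well 40 patients would estimate them.

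**Working it through.** **Inputs.** From section 7.1: n = 40, difference 2 mmHg, SD 2 mmHg, alpha 5%, power 80%. From sections 3 and 3.1.2: one cohort, both tests in each patient. From section 1.1.6: limits of agreement −3.9 to 8.2 mmHg and r = 0.780. Assumed: two-sided testing and one value per patient.

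**Method.** Power is from the noncentral t distribution with n − 1 degrees of freedom and noncentrality 2√n / SD_diff. If the SD of 2 belongs to each test's peak, SD_diff = 2√(2(1 − r)).

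**Attempt to reproduce the plan's figure.**

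| Reading of SD 2 mmHg | SD_diff | n for 80% power | Power at n = 40 |
|---|---|---|---|
| SD of paired differences | 2.00 | 10 (power 0.803; n = 9 gives 0.748) | >99.9% |
| Per test, r = 0 | 2.83 | 18 (0.807) | 99.2% |
| Per test, r = 0.3 | 2.37 | 14 | 99.9% |
| Per test, r = 0.5 | 2.00 | 10 | >99.9% |
| Per test, r = 0.78 | 1.33 | 6 | >99.9% |
| Per test, r = −1 (mathematical limit) | 4.00 | 34 (0.808) | 86.9% |

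No row gives 40. One-sided testing lowers the first two sizes to 8 and 14. Asking for 90% power raises them only to 13 and 24.

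**What would make 40 correct.** Solving for 80% power at n = 40 and 2 mmHg gives SD_diff = 4.40 mmHg. The largest SD_diff that two peaks with SD 2 each can have is 2 + 2 = 4.0. An SD_diff of 4.40 corresponds to limits of agreement 3.92 × 4.40 = 17.3 mmHg wide, against 8.2 + 3.9 = 12.1 mmHg in section 1.1.6.

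**Two independent groups.** The t-test needs 17 per group (34 in total, power 0.807). Two groups of 20 give 86.9%, so this reading does not return 80% at 40 either.

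**SD implied by section 1.1.6.** (8.2 + 3.9) / 3.92 = 3.09 mmHg. This needs n = 21, and power at 40 is 97.9%.

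**Difference detectable at n = 40 with 80% power.** 0.91 mmHg at SD_diff 2, and 1.40 mmHg at 3.09.

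**Precision at n = 40**, with t(39) = 2.023:

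- Bias: 2.023 × s / √40. This is 0.64 mmHg at s = 2 and 0.99 mmHg at s = 3.1.
- Each limit of agreement: 2.023 × s × √(1/40 + 1.96²/78). This is 1.10 mmHg at s = 2 and 1.71 mmHg at s = 3.1.
- Correlation of 0.78, by Fisher's z: 1.045 ± 1.96/√37 = 1.045 ± 0.322, which back-transforms to 0.62 to 0.88.

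**The case against.** **There is a route to 40.** An unpaired formula with attrition reaches it: 32 in total by the normal approximation, and 32/0.80 = 40; or 34 by the t-test, and 34/0.85 = 40. This may be where the number came from. But section 7.1 states neither two groups nor an allowance, and the formula does not suit one cohort in which both peaks are measured on the same day. It may explain the figure but does not support it.

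**"At least 80%" would be true.** Forty patients do exceed 80% on every paired reading in the table. But section 7.1 says that 40 is based on an 80% calculation, and that does not describe a power above 99%.

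**The range 10 to 18 is not the full range.** This stands as a caveat. It covers the SD of differences and the per-test SD at r = 0. Under section 3.1.2 the last mDTC reading also serves as the first WDT reading, and section 1.1.6 cites r = 0.780, so positive correlation is expected and the per-test figure would fall below 18. The r = 0 and r = −1 rows are bounds only.

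**The 3.09 mmHg figure is soft.** This also stands. It assumes normal differences. With a mean of (8.2 − 3.9)/2 = 2.15 mmHg it predicts 76% of WDT peaks higher and 39% of differences within ±2 mmHg, where section 1.1.6 reports 82% and 52.5%. That cohort had a washout from topical treatment and was reported by eyes and tests. The figure serves as one end of a range and nothing more.

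**It is a pilot, and the error is in the safe direction.** Both are true and limit the severity. A pilot may rest its size on precision or feasibility, but this one cites a power calculation, which should then reproduce.

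**Conclusion.** The stated basis for 40 patients is wrong as written. Two-sided and paired, the inputs in section 7.1 need 10 patients if 2 mmHg is the SD of differences, and at most 18 if it is the per-test SD and the correlation is not negative. Power at 40 is above 99% in both cases, not 80%. Even a correlation of −1 would need only 34. The conclusion does not depend on the 3.09 mmHg figure, which would need 21.

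The trial is not underpowered for the mean difference, and no patients need to be added. Two things remain: a justification that cannot be checked, resting on an undefined and unsourced SD, and no statement of precision for the limits of agreement or the correlation. This should be fixed, but it does not threaten the study. The precision figures assume one value per patient, roughly normal differences and all 40 patients analysed.

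**What to change.** Keep n = 40 and replace the power sentence in section 7.1 with a paired precision statement, for example:

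> Each patient has both tests. Assuming an SD of paired differences of 2 to 3.1 mmHg and one value per patient, 40 patients give 95% confidence interval half-widths of about 0.6 to 1.0 mmHg for the mean bias and 1.1 to 1.7 mmHg for each limit of agreement. A correlation of 0.78 would have a 95% confidence interval of about 0.62 to 0.88.

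Label both ends of the SD range as assumptions and give their origin: the upper end comes from the limits of agreement in section 1.1.6, and the sponsor should source the lower end. Section 3.1.2 has both eyes assessed, so one value per patient is a condition of these figures that the authors must confirm.

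If a power figure is kept, call the SD the SD of paired differences and state the paired power for 2 mmHg at 40 patients: above 99.9% at SD 2 and about 98% at SD 3.1. If 40 includes an attrition allowance, say so.

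The cost is protocol wording, with no extra patients or visits. The upper end of the SD range is less favourable than the value now stated.

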7.2 Recruitment

Recruitment sources will include:

- opportunistic recruitment in glaucoma clinics at ICHNHST
- electronic search of the patient database at the ICHNHST. The search criteria will include patients with a diagnosis of 'Primary open-angle glaucoma'. Potential patients will be contacted by telephone by a member of the usual care team and given the opportunity to receive more information about the research that we are undertaking.

Study data and all appropriate documentation will be stored for a minimum of 10 years after the completion of the study.

7.3 Follow-up

Data generated as part of patients' routine clinical care in their usual clinic will be accessed for 18 months following the study. We will include for OCT scans, Visual Field tests, mDTCs and WDTs, with a maximum interval of 6 months each. Permission to access the relevant data will be documented in the informed consent form; patients will be informed that this is optional.

7.4 Data analysis

7.4.1. Data Collection

Data collection will occur solely on the premises of ICHNT and stored on secure Trust computers.

7.4.2 Data Management

. All identifiable study data will be pseudonymised by way of assignment of Study ID to each participant. Electronic data will be housed on trust protected dedicated servers while any hard copy data e.g. consent forms will be kept in dedicated locked cabinets at the ICORG Clinical Trials Unit at the Western Eye Hospital.

7.4.3 Statistical analysis

No interim analyses will take place as part of this pilot study. Data will be acquired using integrated Heidelberg® software packaged with the Heidelberg® Spectralis OCT system. Data for this initial pilot study will be collected using Microsoft® Excel, and analysed using R and GraphPad prism to compare IOPs between the mDCT and WDT.

Specific analyses will include:

- Generation of baseline data including mean and standard deviation of baseline characteristics
- Bland-Altman agreement analysis of the primary outcome
- Correlation analysis between WDT and rate of progression.
- Analysis of change in OCT measurements
- Change over time analysis for secondary outcomes compared to baseline

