3.1 STUDY OUTCOME MEASURES

- **Primary outcome measure:**

Intraocular pressures measured during the mDTC
Intraocular pressures measured during the WDT

- **Secondary outcome measures:** postural blood pressure, heart rate, pupil diameter, pulse oximetry, OCT imaging parameters (angiography and anterior segment angle size) including current and future rates of progression using nerve fibre layer thickness on optical coherence tomography (OCT) and visual field testing.

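### Section 7.4.3 plans to correlate the WDT with a rate of progression, without weighting or a longitudinal model; this costs little if follow-up is regular, but up to about half the variance if many patients have short scan series

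*Combined protocol and SAP*

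**What the plan says.** Section 1.2 hypothesises that peak IOP during the WDT is associated with the rate of progression on OCT, and section 2 makes predictive value for progression the secondary objective. The outcome in section 3.1 is "current and future rates of progression using nerve fibre layer thickness on optical coherence tomography (OCT") together with visual field testing. The whole analysis is one line of section 7.4.3: "Correlation analysis between WDT and rate of progression". Nothing says how the rate is computed, how many scans it needs, whether rates are weighted, or how two eyes are combined, although section 3.1.2 assesses both.

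Section 6 describes the follow-up data as information "which is routinely generated as part of the glaucoma care pathway", and adds: "Participation is optional, and patient's decision (whether or not to grant access to the data) will be documented in the informed consent form". Section 7.3 sets the window at 18 months and says that scans and fields will be included "with a maximum interval of 6 months each". Section 7.1 plans 40 patients, justified by the IOP peak comparison. No figure is given for the progression analysis, for scan error, for the spread of true slopes, or for the expected number of scans.

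**The concern.** Correlating the WDT with a rate takes two stages: estimate a slope for each patient, then correlate the slopes with the WDT. An ordinary correlation gives a slope from two scans six months apart the same weight as one from four scans over 18 months, so the least informative patients can supply much of the scatter. Noise in the slopes also pulls the correlation coefficient towards zero.

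There is little precision to spare. With 40 patients, 80% power and two-sided 5%, the smallest detectable correlation is tanh((1.96 + 0.84)/√37) = 0.43, and optional data access can only reduce the 40. Precision lost in the analysis makes a false finding of no association more likely.

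**Working it through.** **The plan's own figure.** There is none to reproduce for this analysis. The 40 patients of section 7.1 relate to a 2 mmHg difference in IOP peak.

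**Inputs.** From the documents: N = 40, an 18-month window, a 6-month maximum interval. Assumed, because the documents give no values: scan-error SD σ = 1.5–3 µm, true between-patient slope SD τ = 1–1.5 µm/year, and the mix of scan schedules.

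**Precision of one slope.** Error variance = σ²/Σ(t − t̄)², with t in years.
- Scans at 0/6/12/18 months: Σ = 1.25, SE = 0.89σ
- Scans at 0/6/12 months: Σ = 0.5, SE = 1.41σ
- Scans at 0/6 months: Σ = 0.125, SE = 2.83σ

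The error variance of the shortest series is 1.25/0.125 = 10 times that of the fullest. What matters for the analysis is the scatter about the WDT line, v = τ² + σ²/Σ(t − t̄)², and there the ratio is 5 to 9 over the assumed SDs.

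**Cost of equal weights.** If schedule is unrelated to the WDT, the variance of the WDT effect is proportional to mean(v) with equal weights and to 1/mean(1/v) with optimal weights. A mixed model approaches the latter in large samples. The reduction is 1 − 1/[mean(v) × mean(1/v)].

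**Example.** σ = 2, τ = 1, last scan at 18/12/6 months in 80/15/5% of patients:
- v = 4.2, 9 and 33
- mean(v) = 3.36 + 1.35 + 1.65 = 6.36
- mean(1/v) = 0.1905 + 0.0167 + 0.0015 = 0.2087
- reduction = 1 − 1/(6.36 × 0.2087) = 25%

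Here two patients in 40 supply 1.65/6.36 = 26% of the total slope variance.

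**Results over the assumed SD ranges**

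| Follow-up pattern | Variance reduction |
|---|---|
| All at 0/6/12/18 months | 0% |
| Irregular, gaps at most 6 months, series lasting 12–18 months | about 0–5% |
| 70% to 18 months, 30% stopping at exactly 12 | 5–14% |
| Irregular, gaps of 3–6 months, series may stop from 6 months | 10–21% |
| 80/15/5% with last scan at 18/12/6 months | 15–28% |
| 60/25/15% | 27–45% |
| 40/30/30% | 35–53% |

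**Check at N = 40.** A one-stage REML model with random intercept and slope was simulated (150 runs per cell) and compared with unweighted slopes, at (τ, σ) = (1,1), (1,2) and (2,2). These pairs extend beyond the range above, so the large-sample value for the same pairs is given too.

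| Pattern | Simulated | Large-sample |
|---|---|---|
| All 6-monthly | 0, 0, 0% | 0, 0, 0% |
| 80/15/5% | 5, 22, 18% | 15, 25, 15% |
| 60/25/15% | 30, 44, 16% | 27, 41, 27% |
| 40/30/30% | 9, 43, 32% | 35, 49, 35% |

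Most simulated gains are somewhat below the formula, as expected when the variances must be estimated from few scans. The individual cells carry noticeable Monte Carlo error.

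**The case against.** The strongest objection is the interval rule in section 7.3. If gaps are at most six months and patients continue for the full window, slopes are nearly equally precise and the choice of method hardly matters. That is correct, and it is why no single percentage can be put on the loss. A reader might infer that a mixed model would cut the variance by a third to a half. The documents do not support that as a fact: it needs a schedule with many short series, which the plan neither states nor implies.

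The rule does not remove the concern, however. Scans at 0 and 6 months satisfy a 6-month maximum without spanning 18 months. The follow-up is routine care in which participants have nothing to do for the study (section 3), so the study cannot enforce the interval. If the rule works as a filter on what is included, a patient with one long gap may lose the later scans. Series may also be cut short by loss of capacity (section 4.3) or by the exclusion for surgery or laser during the evaluation period (section 4.2). Finally, section 3.1 includes current rates, which would draw on scans before the visit; section 7.3 does not govern those.

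A second objection is that the plan never says the correlation is unweighted. That also stands: equal weighting is the natural reading of the line, not a stated choice. The defect is a method left unspecified whose default form can waste precision.

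Third, this is a secondary question in a self-described pilot, and it will be imprecise under either method. That limits how much the change can achieve, but it is no reason to prefer the less efficient analysis.

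**Conclusion.** The point holds in conditional form. The loss from an unweighted correlation is about 0–5% of variance if gaps of at most six months continue for 12 to 18 months, or 5–14% if three in ten patients stop at exactly 12 months. It rises to about 15–28% with 5% of patients on two scans and 15% stopping at 12 months, and to about 35–53% with 30% and 30%. Those last two ranges are equivalent to 1/(1 − 0.15) = 1.18 to 1/(1 − 0.28) = 1.39 times, and 1/(1 − 0.35) = 1.54 to 1/(1 − 0.53) = 2.13 times, as many patients.

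All of this rests on the assumed SDs and schedules and on a large-sample formula; somewhat smaller gains are likely at N = 40. A tenfold difference in precision between patients might also be inferred, but that figure covers scan error alone. The documents show that uneven follow-up is possible, not that it will occur. The change is still worth making, because it costs little and loses essentially nothing if follow-up proves regular.

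**What to change.** In section 7.4.3, replace the correlation for the progression hypothesis by a linear mixed model of NFL thickness, and likewise of visual field MD:
- fixed effects: actual time since the study visit, WDT peak, and time × WDT peak;
- random intercept and slope per patient, plus an eye-within-patient random effect if both eyes are used;
- every available scan at its true date;
- the time × WDT peak coefficient reported with its confidence interval, as the answer to the hypothesis.

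State also whether scans from before the visit enter the model, since section 3.1 refers to current as well as future rates.

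The cost is analysis wording and slightly more work; R is already named and no new data are needed. The model may fail to converge with few scans per patient, so name the fallback in advance: a precision-weighted regression of per-patient slopes on WDT peak. If follow-up turns out regular, there is no gain in precision.
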